**Background:**

Stiff-knee gait is a common abnormal gait pattern after stroke, characterized by limited knee flexion during the swing phase, which affects walking speed, gait symmetry, and participation in daily activities. botulinum toxin (BoNT) injection in the rectus femoris is considered a standard treatment; however, studies have shown its effects are limited, and it is recommended to combine BoNT injection with rehabilitation training. Robot-assisted gait training (RAGT) provides repetitive, task-oriented gait correction training, but its combined effect with botulinum toxin still requires further investigation.

**Aim:**

This study aims to investigate the effect of combining BoNT injection in the rectus femoris with exoskeleton robot training on stiff-knee gait in stroke patients.

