**Methods:**

A crossover randomized controlled trial design was used. We recruited adult patients with ischemic or hemorrhagic stroke for more than 3 months, who were able to walk independently with or without device on level ground, but presented with spasticity of the knee extensor muscles. And randomly assigned to either an early injection group or a delayed injection group. Both groups received six weeks of exoskeleton robot-assisted gait training one week after injection (2–3 sessions per week, 40 minutes per session, for a total of 12 sessions) and were followed up at three months post-training. The injection site was then switched. The data were

combined according to whether the rectus femoris was injected: injection group (Group A) and non-injection group (Group B). The primary outcome was knee kinematics, including knee flexion angle and range of motion. Secondary outcomes included muscle strength, muscle tone, functional walking ability (6MWT, mEFA), balance (BBS), and self-efficacy (ABC, NEADL).

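### The aim asks about the combined effect of BoNT and robot training, but on the natural reading of the design Group A versus Group B shows only what rectus femoris injection adds to training

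*Combined protocol and SAP*

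**What the plan says.** The Background presents BoNT into the rectus femoris as a standard treatment, adding that "studies have shown its effects are limited, and it is recommended to combine BoNT injection with rehabilitation training". It then turns to robot-assisted gait training and names the gap: "but its combined effect with botulinum toxin still requires further investigation". The Aim follows from this: "This study aims to investigate the effect of combining BoNT injection in the rectus femoris with exoskeleton robot training on stiff-knee gait in stroke patients". It names no comparator.

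The Methods state that "A crossover randomized controlled trial design was used" and that patients were "randomly assigned to either an early injection group or a delayed injection group". On training: "Both groups received six weeks of exoskeleton robot-assisted gait training one week after injection", with 12 sessions in total and follow-up at three months after training. Then: "The injection site was then switched". The data are pooled for analysis, "combined according to whether the rectus femoris was injected: injection group (Group A) and non-injection group (Group B").

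The Analysis and Statistics section judges treatment outcomes by setting measurements after treatment against those at baseline.

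**The concern.** The Background and Aim lead a reader to expect evidence on what the pair of treatments achieves, or on what robot training contributes once BoNT has been given. The Methods randomise the timing of injection and pool by rectus femoris injection. Training is not a randomised factor.

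Two conclusions could then outrun the design. If A beats B, the stated aim lets this be reported as support for combining BoNT with training, although the same difference would arise if training contributed nothing. If A equals B, it could be reported that the combination does not help, although training after BoNT might still be useful. The planned baseline comparisons add a further route: change from baseline in Group A is the figure most easily labelled the effect of the combination, and it has no control.

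**Working it through.** The documents give no sample size, power or effect size, so there is no figure of the plan's to reproduce. The question is which treatment contrasts the described design can estimate.

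**Inputs (Methods).** Two sequences, early and delayed injection; two periods; rectus femoris injected in one period and not in the other.

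**Assumptions.** Training is given in both periods, and there is no carryover. The period without rectus femoris injection is first taken to have no BoNT.

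**Model.** Mean = μ + R (robot training) + B (rectus femoris BoNT) + I (their interaction) + P (second period).

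- Early, period 1: μ + R + B + I
- Early, period 2: μ + R + P
- Delayed, period 1: μ + R
- Delayed, period 2: μ + R + B + I + P

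There are five parameters and the design matrix has rank 3. R appears in every cell and cannot be separated from μ. B and I always appear together.

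**A minus B.** Averaging over periods, A = μ + R + B + I + P/2 and B-group = μ + R + P/2. The difference is **B + I**, the effect of rectus femoris injection given training.

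**Estimability, with a sensitivity case in which period 2 has no training:**

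| Question | Contrast | Training in both periods | No training in period 2 |
|---|---|---|---|
| Rectus femoris BoNT added to training | B + I | yes | yes |
| Training added to BoNT (both versus BoNT alone) | R + I | no | no |
| Synergy | I | no | yes |
| BoNT alone versus neither | B | no | yes |
| Training alone versus neither | R | no | no |
| Both versus neither | R + B + I | no | no |

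In the sensitivity case, training is present throughout period 1 and absent throughout period 2, so its effect is confounded with period. B and I become estimable from the between-group differences in each period.

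**What a given difference can hide (assumed figures).** Suppose A minus B is 5 degrees.

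- R = 0, B = 5, I = 0: A minus B = 5 + 0 = 5; training adds R + I = 0 to BoNT.
- R = 10, B = 5, I = 0: A minus B = 5 + 0 = 5; training adds 10.
- R = 0, B = 0, I = 5: A minus B = 0 + 5 = 5; all of it is synergy.

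With training in both periods, the A versus B data cannot tell these apart.

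**If the other period includes BoNT at another site.** Let E be the effect of that injection given training. A minus B becomes (B + I) − E, which is rectus femoris injection versus injection elsewhere, both with training. The training-only condition is then never observed.

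**The case against.** The strongest reply is that the aim already admits the add-on question. Read with the definition of Groups A and B in the Methods, it asks what rectus femoris injection does in patients who are being trained, and the design addresses that. Nowhere do the documents claim synergy, superiority over BoNT alone, or a benefit of training. This stands: the trial is informative, and the possible over-reading lies in a future report. It does not remove the point. The aim has no comparator, the Background frames the gap around training's combined effect with BoNT, and the analysis relies on change from baseline, so the plan leaves room for the wrong conclusion.

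The second reply concerns the facts. The Methods describe one six-week course of 12 sessions (6 weeks × 2 sessions = 12) and then the switch. They do not say that training is repeated. A reader might infer that every patient is trained in both periods, and that synergy is therefore beyond reach whatever the sample size. The documents do not support stating that without condition: with an untrained second period and no carryover, the interaction would be estimable. Training added to BoNT would still not be.

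The third reply is that switching the injection site may mean BoNT elsewhere in the other period. This also stands. A reader might count exactly two of the four possible conditions as observed, training only and both, but that count is not established. The ambiguity makes naming the comparator more necessary.

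**Conclusion.** The concern holds in a limited form. The Background and Aim ask about a combined effect, while the Methods vary only rectus femoris injection. With training in both periods and no carryover, one of the six contrasts examined is estimable: rectus femoris injection given training. Training added to BoNT, which is the combination against standard BoNT, is not estimable whether or not the second period is trained. The statement about synergy depends on training being given in both periods. If BoNT is injected elsewhere in the other period, the contrast shrinks to one injection site against another.

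A reader might go further and infer that the trial cannot answer its aim at all. The documents do not support that, because the add-on reading of the aim is legitimate and the A versus B contrast serves it. This is a matter of design and interpretation, with no numerical error, and it should be corrected in the wording of the aim and conclusions.

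**What to change.** 1. Restate the aim along these lines: *to estimate, in patients with stiff-knee gait after stroke who all receive the same exoskeleton training, the effect of BoNT injected into the rectus femoris compared with no rectus femoris injection.*
2. Reconcile the Methods on two facts for each period: what, if anything, is injected when the rectus femoris is not, and whether the training course is given. If either differs from the assumptions behind the restated aim, name the comparator accordingly.
3. Limit the conclusion to the between-condition A versus B contrast.
4. State in Analysis and Statistics that change from baseline within Group A is descriptive. It is not evidence of the effect of the combination, or of training over BoNT alone.

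No arm, patient or visit is added. The cost is a narrower claim and a restricted interpretation of the baseline comparisons that the plan already includes.

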**Participants:**

Inclusion criteria : We will recruit adult patients with ischemic or hemorrhagic stroke for more than 3 months, are able to walk independently with or without device on level ground (Functional Ambulation Category  $\geq 4$ ) (Holden et al., 1984) but have inadequate of knee flexion during the swing phase. Their affected RF has spasticity with the modified Ashworth scale between 1+ and 2. (Rw & Smith, 1987). Patients are BoNT-A treatment-naive or treated with BoNT-A  $\geq 4$  months in the affected leg before recruitment. Patients receiving oral muscle relaxants or other medication for spasticity were on a stable dose for  $\geq 2$  months before recruitment. They can obey simple order.

Exclusion criteria : participation in other trials; fixed contractures or bony deformities in the affected leg; previous treatment of the affected leg with neurolytic or surgical procedures( such as, phenol block, tendon lengthening of transfer, tenotomy, muscle release, arthrodesis); severe cardiovascular comorbidity (recent myocardial infarction, heart failure, uncontrolled hypertension, orthostatic hypotension), known sensitivity to BoNT-A, had an infection of the skin, soft tissue in the injection area; are pregnant.

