**Analysis and Statistics:**

All data were analyzed using IBM SPSS Statistics version 26.0 for Windows. Prior to selecting appropriate statistical tests for continuous variables, the Shapiro-Wilk test was conducted to assess the normality of data distribution. For variables exhibiting a normal distribution, independent samples t-tests or paired samples t-tests were applied. For non-normally distributed data, the Mann-Whitney U test or the Wilcoxon Signed Rank test was used instead. Treatment outcomes were assessed by comparing post-intervention time points with baseline measurements.

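### Time since stroke is used only for eligibility in a long crossover open from just over 3 months; this can cost precision, not validity, and using it is a minor improvement

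*Combined protocol and SAP*

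**What the plan says.** The Participants section sets a lower limit on time since stroke, "adult patients with ischemic or hemorrhagic stroke for more than 3 months", and no upper limit. It asks for stable antispastic medication and a gap since any earlier toxin treatment, but sets no condition on stability of recovery.

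The Methods section states that "A crossover randomized controlled trial design was used" and that patients were "randomly assigned to either an early injection group or a delayed injection group". It names no stratification factor, block size or allocation ratio. On timing it says "Both groups received six weeks of exoskeleton robot-assisted gait training one week after injection" and that patients "were followed up at three months post-training", after which "The injection site was then switched". The length of the second period is not given separately. The data are then "combined according to whether the rectus femoris was injected: injection group (Group A) and non-injection group (Group B").

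The Analysis and Statistics section lists independent and paired t-tests, with Mann-Whitney U and Wilcoxon signed-rank tests as alternatives. It adds that "Treatment outcomes were assessed by comparing post-intervention time points with baseline measurements", without saying whether baseline means trial entry or the start of each period. No period, sequence or covariate term appears.

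**The concern.** A crossover gains precision because each patient serves as their own control. That gain shrinks when patients change between periods for reasons unrelated to treatment, and by different amounts. A patient entering at about 13 weeks after stroke may still be recovering in period 1 and less so in period 2. A patient years after stroke probably changes little in either. The entry rule allows both.

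A period term would remove the average drift but not the difference in drift between recent and chronic patients. That difference stays in the residual variance of the primary knee measures. If recent patients fall unevenly between the two sequences by chance, it also shifts the estimate in that particular trial. Time since stroke has to be known to check eligibility, so the information is available and unused.

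**Working it through.** The plan gives no sample size, SD, effect size or recovery rate, so there is no figure to reproduce. The durations below come from the Methods section. Everything in degrees is an assumption.

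**Duration.** The short count is 6 weeks of training plus 12 of follow-up, or 18 weeks. The long count is 1 + 6 + 13 = 20 weeks. Two such periods take 36 to 40 weeks, so a patient entering at week 13 finishes at about week 49 to 53. If period 2 stopped at the end of training, the total would be at most 20 + 7 = 27 weeks.

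**Model.** For each patient take y = period 1 change minus period 2 change. Assume n = 20 (10 per sequence), 8 recent patients (p = 0.4) and an SD of 4 degrees for each period's change. Let d be the extra natural gain in period 1 over period 2 in recent patients, and zero in chronic patients. The variance of y without drift is 2 × 4² = 32.

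The injection effect is half the difference in mean y between sequences.
- No use of time since stroke: SE² = 0.25 × 2 × (32 + 0.24d²)/10 = 1.6 + 0.012d².
- Stratified and adjusted, sequences balanced within strata: SE² = 1.6, whatever d is.
- Adjusted only: SE² = 1.6 × E[1/(1 − r²)], where r² = (difference in recent counts)²/96. Splits of the 8 recent patients of 4:4, 5:3, 6:2, 7:1 and 8:0 have probabilities 0.350, 0.480, 0.150, 0.019 and 0.001, counting both directions. The factors are 1, 1.043, 1.2, 1.6 and 3. The expectation is about 1.064, so SE² is about 1.702.

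| d (degrees) | SE, unused | SE, adjusted only | SE, stratified and adjusted |
|---|---|---|---|
| 0 | 1.26 | 1.30 | 1.26 |
| 2 | 1.28 | 1.30 | 1.26 |
| 3 | 1.31 | 1.30 | 1.26 |
| 4 | 1.34 | 1.30 | 1.26 |
| 6 | 1.43 | 1.30 | 1.26 |
| 8 | 1.54 | 1.30 | 1.26 |

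Simulation agrees to within about 0.02. Adjustment alone breaks even at d = √(0.102/0.012) = 2.9 degrees. Below that it costs about 2 to 4% of the SE. At d = 6 the variance ratio is (32 + 8.64)/32 = 1.27.

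**Imperfect classification.** With 20% of patients put in the wrong stratum, simulated adjustment alone at d = 6 moves the SE only from 1.42 to 1.41.

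**Chance imbalance.** A 6:2 split shifts the estimate by 0.5 × (0.6 − 0.2) × d = 0.2d, which is 0.6 to 1.6 degrees for d = 3 to 8. A split that uneven or worse, in either direction, has probability 0.150 + 0.019 + 0.001 = 0.17.

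**The paired test as written.** It has no period term, so its reported variance carries 0.4d² rather than 0.24d². At d = 6 its reported SE is √((32 + 14.4)/20) = 1.52. The step from 1.43 to 1.52 comes from the missing period term, not from time since stroke.

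**Other assumptions.** With the SD of the within-patient difference at 5 to 8 degrees, half the patients recent and drift of 2 to 6 degrees, the excess variance after a period term is 0.25d²/SD². This runs from 2% (d = 2, SD 8) to 36% (d = 6, SD 5).

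**The case against.** The strongest reply is that the gain needs a large drift that nothing in the documents supports. A d of 6 to 8 degrees is 1.5 to 2 times the assumed SD of a period's change. Entry is limited to patients who already walk independently and whose antispastic medication is stable. If baseline is re-measured each period, steady recovery cancels and only slowing recovery remains. If the main assessment falls at the end of training, the relevant window is about 7 weeks rather than 18 to 20. All of this stands, and it is why the size is left open and the priority is low.

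It is also fair that the plan contains no crossover model to which a covariate could be added. Pooling by injection status without period or sequence is a separate and larger defect, and the fix has to state the model it needs. The Methods section describes no randomisation method at all, so unreported stratification cannot be excluded. What can be said is that none is described.

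Two stronger readings are tempting. A reader might infer that early recovery biases the comparison in favour of injection. It does not in expectation: period 1 recovery favours injection in the early sequence and non-injection in the delayed one. A reader might also count the 6:2 imbalance as a harm on top of the lost precision. Averaged over randomisations it is already inside the standard errors above. It describes what that variance looks like in one unlucky trial.

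What survives is that the listed tests cannot use time since stroke, and that stratifying and adjusting costs little at any drift.

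**Conclusion.** The point holds as a minor matter of efficiency. The plan mixes recent and chronic patients without limit and, as described, does nothing with time since stroke after eligibility. The consequence is possible extra variance and chance imbalance, not bias in expectation. Its size depends on unstated quantities: sample size, SD, share of recent patients and how recovery differs between periods. Under the assumptions above it is negligible below about 3 degrees of drift difference and useful at 6. The clearest gain comes from stratifying and adjusting together; adjustment alone can slightly hurt, and it depends on a cut-off that really separates those still recovering. The 36 to 40 weeks assumes that period 2 repeats period 1. The change ranks behind adding an analysis based on period and sequence.

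**What to change.** Keep the entry criterion.

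- **If randomisation is not complete:** stratify the allocation to early or delayed injection by time since stroke, at one cut-off fixed in advance.
- **Primary analysis of the knee measures:** replace the pooled injected-versus-not-injected t-test or rank test with a regression of each patient's period difference on sequence and the time-since-stroke stratum. The period difference is the period 1 change minus the period 2 change, each from that period's own baseline. With sequence coded +1 for early and −1 for delayed, its coefficient is the injection effect; the intercept and stratum terms absorb the period effect and its variation with time since stroke. State that baseline is measured at the start of each period.
- **If randomisation is complete but the data are unanalysed:** pre-state this regression. The Participants section speaks of recruitment in the future tense, while Methods and Analysis are largely in the past, so the trial's status should be made clear.
- **If the data have been seen:** report the regression as a sensitivity analysis, since the covariate can no longer be called pre-stated.

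The cost is one factor in the randomisation list, one degree of freedom, and replacement of the pooled tests by a crossover model, which is needed anyway. Without stratification, expect a standard error about 2 to 4% larger if recovery has levelled off in all patients.

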**Methods:**

A crossover randomized controlled trial design was used. We recruited adult patients with ischemic or hemorrhagic stroke for more than 3 months, who were able to walk independently with or without device on level ground, but presented with spasticity of the knee extensor muscles. And randomly assigned to either an early injection group or a delayed injection group. Both groups received six weeks of exoskeleton robot-assisted gait training one week after injection (2–3 sessions per week, 40 minutes per session, for a total of 12 sessions) and were followed up at three months post-training. The injection site was then switched. The data were

combined according to whether the rectus femoris was injected: injection group (Group A) and non-injection group (Group B). The primary outcome was knee kinematics, including knee flexion angle and range of motion. Secondary outcomes included muscle strength, muscle tone, functional walking ability (6MWT, mEFA), balance (BBS), and self-efficacy (ABC, NEADL).

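### Does the Methods section contradict itself on whether the comparator, Group B, was injected?

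*Combined protocol and SAP*

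**What the plan says.** The injection schedule is described only in the Methods section, in four statements:

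- Allocation, by randomisation: "either an early injection group or a delayed injection group".
- Timing of training, with the follow-up after it: "Both groups received six weeks of exoskeleton robot-assisted gait training one week after injection"; afterwards patients "were followed up at three months post-training".
- Crossover step, described in one short sentence: "The injection site was then switched".
- Pooling for analysis, which defines the two groups compared: "combined according to whether the rectus femoris was injected: injection group (Group A) and non-injection group (Group B".

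The Aim is to study "the effect of combining BoNT injection in the rectus femoris with exoskeleton robot training on stiff-knee gait in stroke patients", and the Background says of robot training that "its combined effect with botulinum toxin still requires further investigation". Neither section names a comparator. On the target muscle, Participants requires RF spasticity, while Methods describes patients who "presented with spasticity of the knee extensor muscles". Neither wording identifies a second injection site or rules one out. Analysis and Statistics lists independent and paired tests with rank-based alternatives, and compares later time points with baseline.

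**The concern.** Taken at face value, the four statements pull in two directions. If both groups start training a set time after an injection, and the site is then changed, everyone has been injected in the first period and there are at least two sites. If one arm is delayed and the comparator data are labelled as non-injected, that arm had nothing in the first period.

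The difference bears on interpretation. If Group B was not injected, the A-B difference is the effect of adding RF injection to robot training. If Group B was injected elsewhere instead, the difference compares the RF with that other site, and Group B's change from baseline includes the effect of the other injection. A reader who took the label literally could then draw the wrong conclusion from a correct number.

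**Working it through.** **Inputs.** The four statements are from Methods and the tests from Analysis and Statistics. The documents give no sample size, effect size, standard deviation or power figure, so there is no stated figure to reproduce. One opening part of the document was not available, so the second site is unnamed only as far as the sections from Background to Analysis and Statistics go.

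**Step 1: do the statements conflict?**

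| Statement | Every word taken literally | Labels taken to refer to the RF |
|---|---|---|
| Training in both groups timed from an injection | both groups injected | both groups injected |
| Site switched | at least two sites | RF and another site |
| Early and delayed arms | delayed arm not injected at first | RF injection comes later in the delayed arm |
| Non-injection label, Group B | Group B not injected | Group B not injected in the RF |

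The middle column cannot all be true; the right-hand column can. The narrower meaning is not forced on the text, because the pooling sentence states its criterion, RF injected or not, immediately before it gives the labels. The RF is also the only injection target that the Aim names. One consistent reading is enough to show that the text is ambiguous and not self-contradictory. It does not establish what was done.

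**Step 2: does group membership depend on the reading?** There are 2 sequences x 2 periods = 4 cells. Taking early and delayed to refer to the RF, or to injection of any kind, gives the same allocation:

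| Sequence | First period | Second period |
|---|---|---|
| Early | RF injected: Group A | RF not injected: Group B |
| Delayed | RF not injected: Group B | RF injected: Group A |

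All 4 cells are assigned by RF status alone. Whatever else Group B received, the same measurements enter the same tests.

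**Step 3: what does the number mean?** Let g be the change with training and time, r the added effect of RF injection and o the added effect of an injection elsewhere. Assume additive effects and set carryover and period effects aside.

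- Group B not injected: A = g + r and B = g, so A-B = r, and Group B's change is g.
- Group B injected elsewhere instead of the RF: A = g + r and B = g + o, so A-B = r - o, and Group B's change is g + o.

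The calculated A-B is one number. Its interpretation differs by r - (r - o) = o. No value for o can be taken from the documents, and none is assumed here.

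**Step 4: how much of the trial is affected?** The unnamed exposure concerns the 2 Group B cells of the 4. Counting from an injection at the start, the first period lasts 1 week + 6 weeks + 3 months (about 13 weeks) = about 20 weeks. This is the extent of the missing description. It does not measure bias.

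**The case for a change.** The strongest reply is that the reading that reconciles all the sentences is also the one on which A-B is not the RF effect by itself. Group B would have been injected at an unnamed site while being called non-injected, and its change from baseline, which Analysis and Statistics says is examined, would not reflect training only. If instead Group B had no injection, the sentence timing training from an injection and the sentence about switching the site do not describe that group correctly, and its training start has no stated reference point. Either way, some wording in Methods is loose.

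That much stands: the supplied text does not let a reader tell which contrast was estimated, and the algebra for the two cases is right. Two points limit it. First, no section attributes Group B's change to training alone or describes A-B as RF injection against no injection, so there is no stated conclusion to correct. Second, the remedy would be to write down exposures already known to the investigators and to label the groups by RF status. The pooling rule already uses RF status, so nothing in the comparison would be computed differently.

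**Conclusion.** The concern does not call for a change to the plan. The Methods wording is ambiguous about the comparator, but it is not shown to contradict itself, because a reading limited to the RF fits all four statements. The analysis is unaffected: group membership is the same in 4 of 4 cells, and the tests and estimates stay as they are. What remains open is the name of the contrast, which shifts by the effect of an other-site injection. The documents do not allow that effect to be quantified.

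This rests on two assumptions: that the data are pooled by RF status as Methods states, and that the investigators hold a record of what was injected in each period. Methods describes the injections in the past tense, so the second is reasonable. The sentences on timing, site and group labels do need to be reconciled with that record when results are reported, and the contrast worded to match. That is a matter of description that the investigators can settle from what they already know. Nothing here implies that one site or schedule is the right one.

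### Two unranked primary knee measures, no primary visit, alpha or multiplicity rule, and the injected-versus-not-injected comparison is never named as the deciding test

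*Combined protocol and SAP*

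**What the plan says.** All references are to the combined protocol and SAP.

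- **Outcome (Methods).** "The primary outcome was knee kinematics, including knee flexion angle and range of motion". Neither measure is placed first, and no gait phase is attached to them. The Background and Participants sections describe the deficit as too little knee flexion in swing.
- **Aim.** To study "the effect of combining BoNT injection in the rectus femoris with exoskeleton robot training".
- **Design (Methods).** "A crossover randomized controlled trial design was used". On training: "Both groups received six weeks of exoskeleton robot-assisted gait training one week after injection". Patients "were followed up at three months post-training", after which the text says the site of injection was changed over. The data were then "combined according to whether the rectus femoris was injected: injection group (Group A) and non-injection group (Group B").
- **Tests (Analysis and Statistics).** For normally distributed variables, "independent samples t-tests or paired samples t-tests were applied", with rank-based equivalents otherwise. None is assigned to an outcome, a visit or a contrast.
- **Comparison (Analysis and Statistics).** "Treatment outcomes were assessed by comparing post-intervention time points with baseline measurements".

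The sections available for review (Background to Analysis and Statistics) give no primary visit, significance level, success rule or multiplicity rule.

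**The concern.** A reader cannot tell which result decides the trial, for two reasons.

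First, there are at least two candidate primary results. With no ranking, no visit and no correction, a claim could rest on whichever measure, or whichever visit, happens to be significant. The false-positive rate of such a claim exceeds that of a single test.

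Second, the contrast that answers the aim is not the one put into words. The question is what the rectus femoris injection adds, and that needs injected against not injected. A change from baseline within a condition mixes any injection effect with whatever the training produces. If such a change were reported as the trial's result, an effect of training could be read as an effect of the injection.

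**Working it through.** The plan states no alpha, power or sample size, so there is no figure of its own to reproduce. The check has two parts.

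**Part 1: which contrast decides**

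1. The aim and the pooling into Groups A and B point to a comparison between conditions. The independent-samples tests fit that reading, since they compare groups.
2. The paired tests could serve either a within-patient comparison of A with B or a before-and-after comparison. The text does not say which.
3. The one comparison stated in a sentence is post-intervention against baseline.
4. Both groups train after injection. The changeover of injection site also leaves open that Group B was injected somewhere other than the rectus femoris. Change from baseline in Group A therefore contains training plus any rectus femoris effect. In Group B it contains training plus, possibly, the effect of an injection elsewhere. Neither change alone isolates the rectus femoris injection.

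**Part 2: false-positive rate when either measure can carry the claim**

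Inputs:
- Two measures: from the Methods.
- Two-sided 5% per test: assumed.
- No injection effect: the null hypothesis being examined.
- Any one significant A-versus-B result counts: assumed, because no success rule is given.
- Correlation between test statistics, 0 to 0.9: assumed range.
- One or two primary visits: assumed. The analysis section speaks of time points in the plural, but three months after training is the only follow-up time stated.

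Formula at zero correlation, with k tests: 1 − 0.95^k.

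- k = 2 (one visit): 1 − 0.95² = 9.75%.
- k = 4 (two visits): 1 − 0.95⁴ = 18.5%.

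For positive correlation r, the rate is the probability that at least one of k correlated standard normal statistics exceeds 1.96 in absolute value. It was obtained by numerical integration for k = 2. For k = 4 it was simulated, with r between measures, r between visits, and their product for pairs that differ in both.

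| r | 2 measures, 1 visit | 2 measures, 2 visits |
|---|---|---|
| 0 | 9.8% | 18.5% |
| 0.5 | 9.1% | 16.1% |
| 0.7 | 8.4% | 13.7% |
| 0.9 | 7.0% | 9.8% |

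If all four tests instead share one common correlation of 0.9, the last entry is 9.4%.

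These rates count significance in either direction. Counting only results that favour injection, the nominal rate is 2.5%:

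- One visit: 1 − 0.975² = 4.9% at r = 0, falling to 3.5% at r = 0.9.
- Two visits: 1 − 0.975⁴ = 9.6% at r = 0, falling to 4.9% at r = 0.9.

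**Cost of a Bonferroni split over two measures**

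A two-sided 5% test with 80% power has an expected statistic of 1.960 + 0.842 = 2.802. At two-sided 2.5% the critical value is 2.241, so power is Φ(2.802 − 2.241) = Φ(0.560) = 71.2%. Restoring 80% needs ((2.241 + 0.842) / 2.802)² = 1.21 times the patients.

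**The case against.** The strongest reply is that the A-versus-B comparison is plainly intended. The data are pooled into those two groups, independent-samples tests are listed, and the sentence about baseline may only define outcomes as change scores. Much of this stands. A reader might infer that the plan makes change from baseline its primary test, but the documents do not support that. They leave the deciding test unnamed. The gap matters because the same wording would also permit a within-condition result to be presented as the finding.

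A reader might also infer that Group B is robot training alone, so that a change from baseline shows what training does without any injection. The changeover of injection site leaves room for an injection elsewhere in Group B, so that reading is not established. The narrower statement survives under either reading: change from baseline cannot isolate the rectus femoris injection.

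A third reply is that the two-visit range depends on a second primary visit that the plan does not establish, since the plural time points could be one per crossover period. That is right. Zero correlation is also implausible for two measures of one joint, so the lower half of each range is the realistic part. If both measures had to be significant there would be no inflation, but the plan does not say so.

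Finally, much larger error rates can be produced by assuming a sample size and a training effect and counting within-condition changes as successes. The documents give neither quantity and state no such rule, so no figure of that kind is relied on here.

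**Conclusion.** The point holds and should be corrected. The primary outcome names two unranked measures with no visit, alpha or multiplicity rule, and the contrast that answers the aim is implied but not designated. The inflation is moderate: up to about twice the nominal rate at one visit. The two-visit figures apply only if a second primary visit is allowed. All the rates rest on 5% tests and an any-one-counts rule, neither of which is in the documents. They describe what the wording permits, not what the trial did.

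The more consequential part needs no arithmetic. The only comparison the analysis section words cannot by itself show an effect of the rectus femoris injection, so a conclusion drawn from it could be wrong even with a single measure at a single visit.

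**What to change.** 1. Name one primary measure at one stated visit. Swing-phase knee flexion of the affected leg would match the deficit described in the Background, if it can be derived from the recorded kinematics. The documents do not say whether it can.
2. Test it by one within-patient comparison of rectus femoris injected versus not injected, adjusted for period, at two-sided 5%.
3. Test range of motion next in fixed order, only if the first test is significant. Alternatively, keep both measures as primary with Holm or Bonferroni.
4. State that within-condition changes from baseline are descriptive and do not support a claim about the injection.
5. State what Group B received, so that the contrast can be interpreted.
6. The text is largely in the past tense. If outcomes have already been examined, disclose the choice as post hoc and report both measures at all visits with corrected p-values.

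**Cost.** This is mainly wording, provided the chosen measure can be derived. In fixed order, success on range of motion alone no longer counts. With Bonferroni, a test with 80% power falls to about 71%, or needs about 21% more patients. Making baseline changes descriptive gives up an easier route to a significant result. If outcomes have been seen, new wording cannot make the choice pre-specified.
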